Furthermore, the impact on the result of social inequality will be thoroughly examined.

METHOD

Project design

This study is designed as a prospective registry-based observational study using modelled air/noise pollution data. The population is predominantly males from two Danish clinical trials (DANCAVAS and VIVA trials)

Study population

DANCAVAS I and II (41-43) are two similar population-based randomized, multicentered, clinically controlled studies designed to evaluate the benefits of 7-step multiple cardiovascular screening and modern vascular prophylaxis in a population of men and a small subpopulation of females, aged 60-74 years, living in the southern part of Denmark. For each participant, all relevant CVD risk factors were measured or determined.

The screening included (figure 1): 1) low-dose non-contrast CT scan to detect CAC and aortic/iliac aneurysms, 2) ankle-brachial blood pressure index (ABI) to detect peripheral arterial disease (PAD) and hypertension, 3) a telemetric assessment of the heart rhythm, and 4) a measurement of the cholesterol and plasma glucose levels.

The Viborg Vascular (VIVA) screening trial (44) is a randomized, multicentered, population-based clinically controlled study designed to evaluate the benefits of vascular screening and modern vascular prophylaxis in men between 65-74 years of age living in the region of Mid Denmark (Viborg County). For each participant, abdominal ultrasound scanning of the infrarenal aorta were performed to detect abdominal aortic aneurism (AAA), and ABI were measured to detect PAD and hypertension (45). In all, 18,749 men were screened.

A total of 33,723 participants in the age of 60-74 are included from the two cohorts. In both trials, an AAA was defined as maximal infrarenal diameter of 30 mm or more, and PAD was defined as an ABI < 0.90 or ≥ 1.40 using the same validated hand held Doppler-based methodology (46). We have accounted for traditional CVD confounders in all participants. This is unique for our study. Previous studies on air pollution and CVD burden have not been able to prospectively consider these confounding variables to the same extent.

Air pollution

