In Denmark a validated and reliable air pollution model system is available (figure 2). The system is named DEHM/UBM/AirGIS (28, 30-32) and consists of three coupled models; the Danish Eulerian Hemispheric Model (DEHM) (28, 32), the Urban Background Model (UBM) (29) and the Operational Street Pollution Model (OSPM) (30, 31) and a GIS system (AirGIS) that couples the modelled concentrations with the address level of the population. The system calculates air pollution concentrations of 80 chemical species as well as air pollution levels in cities, in streets and on address level even on both side of the street. These pollution levels can be calculated back to 1979 giving retrospectively data 40 years back. The model system is validated in relation to air pollution measurements throughout Denmark back to 1990 with high correlation between model estimated values and measured values (28, 30, 31, 47). This multi-scale model system is unique, capable of running on very high temporal (hourly) and spatial (address level) resolutions. The development of the models and the calculation of air pollution and measurements is performed at Aarhus University, Department of Environmental Science (ENVS). The model is robust; taking all necessary factors into account that could contribute to the individual life-long air pollution exposure and the model is one of the best in the world.

Noise pollution

Noise is calculated using state-of-the-art algorithms implemented in a well-known software, the SoundPLAN. The algorithms, reflecting advanced physics and mathematics-based knowledge, consider the propagation of sound in the atmosphere as well as the sound originating from the source, e.g., road transport, railway. Here, information from various national registers, such as the national traffic database, including traffic counts, travel speeds, the building register, the address register, and the Danish surface and elevation model, to name a few. In addition, advanced weather classes reflecting all meteorological conditions in Denmark are used in noise calculations. The model output is a noise estimate at the address location or any location of interest in Denmark, which can be subsequently used to investigate the health impacts of short-term and/or long-term noise exposure (48, 49).

Statistics

The entire study population is monitored until December 31. 2022, in the Danish national registers.

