Primarily a multivariate Cox proportional hazards regression model will be used to examine the associations between air- and noise pollution and all-cause mortality and CVD morbidity and mortality when adjusting for inclusion date, sex, and other potential confounding factors at baseline.

Descriptive statistics of the main study variables to examine noise pollution will be presented in tables, frequencies with percentages of dichotomous/ordinal variables and medians with quartiles for numeric variables. Outcomes will be analyzed both as dichotomized variables, present CAC, severe CAC (CAC score above 400), AAA and PAD, and as the underlying continuous variables, CAC score, aortic diameter, and lowest measured ankle-brachial blood pressure index. Confounding CVD variables will be considered and adjusted for (e.g., lifestyle, medical history, QoL, weight,

height, waist circumference, blood pressure, ABI, calcium score for coronary arteries, aortic dimensions, HbA1c and lipid parameters).

To investigate hypothesis about noise we will, for each dichotomized outcome, estimate adjusted odds ratios using multivariable logistic regression, with cumulated noise pollution as exposure and the Framingham risk factors as confounders. The continuous variables will be analyzed in multivariable linear regression models and the cardiovascular risk factors as confounders.

To investigate the impact of work versus home address, we will compare regression models with accumulated air pollution from both work and home addresses with models with air pollution only from home addresses. ROC curves from both models will be compared to evaluate the hypothesis.

Ethics approval and consent

The DANCAVAS and VIVA studies were approved from “Videnskabsetisk Komité” (S20140028, S20160164 and M20080028). Access to the participants’ former residential addresses has been approved from “Sundhedsdatastyrelsen” (FSEID-00005213).

Feasibility

We have formed the group of researchers that will perform the study and we have received all the necessary approvals. The group includes professors in the areas where special skills are needed.

COLLABORATION

This project is a collaboration across disciplines and sectors (cardiology, physics, environmental sciences, surgery, public health). The study will be performed as a collaboration between:

- Cardiovascular Research Unit, Odense University Hospital - Svendborg; [name] and [name]

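### The noise models for aortic diameter and AAA name only risk factors as confounders and no trial-cohort term, although cohort, region and aortic imaging (CT v ultrasound) coincide.

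*Protocol*

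**What the plan says.** The Protocol's Statistics section gives the noise analyses their own confounder sets. The logistic models for the dichotomised outcomes (any CAC, severe CAC, AAA, PAD) are to be fitted "with cumulated noise pollution as exposure and the Framingham risk factors as confounders". For the underlying continuous outcomes, "CAC score, aortic diameter, and lowest measured ankle-brachial blood pressure index", the text is: "The continuous variables will be analyzed in multivariable linear regression models and the cardiovascular risk factors as confounders".

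The same section has a broader, open-ended statement, "Confounding CVD variables will be considered and adjusted for". Its examples are all participant characteristics or measurements, such as lifestyle, medical history, blood pressure and lipids. Inclusion date, at best a partial stand-in for trial, is named only for the Cox model: "when adjusting for inclusion date, sex, and other potential confounding factors at baseline". Trial, region and imaging method are not named as a covariate or stratum, and no by-cohort analysis is described.

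Under Study population, DANCAVAS participants live in southern Denmark and had a "low-dose non-contrast CT scan to detect CAC and aortic/iliac aneurysms". VIVA participants live in Viborg County, Mid Denmark, and had abdominal ultrasound of the infrarenal aorta. Both trials define AAA by the same 30 mm threshold and measure ABI with the same Doppler method. The two cohorts are given one total of 33,723, and 18,749 men were screened in VIVA.

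**The concern.** Cohort, region and aortic imaging method are one and the same split here. A systematic difference between CT and ultrasound readings, or a regional difference in diameter, would therefore appear as a difference between cohorts. Noise is modelled by place ("The model output is a noise estimate at the address location or any location of interest in Denmark"), so mean exposure can also differ between the cohorts. When both differences are present and the model has no cohort term, part of the cohort difference in diameter is credited to noise.

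The named covariates do not protect against this. No Framingham or other cardiovascular risk factor records which instrument measured the aorta. The shared 30 mm definition fixes the cut-off for AAA but not the measurement compared with it, and diameter has no cut-off at all.

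At stake are two named noise outcomes. The bias can go in either direction. It does not shrink as the sample grows, whereas the standard error does, so at this sample size a small offset can produce a significant slope.

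**Working it through.** The Protocol states no effect size, power or error rate for these models, so there is no figure of its own to reproduce. The calculation shows how a given offset would translate into a false noise association.

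**Inputs from the Protocol (Study population).** N = 33,723 and VIVA = 18,749. If all screened VIVA men are included, DANCAVAS = 33,723 − 18,749 = 14,974. The VIVA share is p = 18,749/33,723 = 0.556, and p(1−p) = 0.247. If only 90% or 80% of the VIVA men were included in the same total, p(1−p) would be 0.250 or 0.247, so the results barely move.

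**Assumptions, none of them in the documents.** Diameter SD (s) of 3 or 4 mm; offset δ between cohorts in measured diameter; difference D between cohorts in mean noise, in within-cohort SDs; no true noise effect; two-sided 5% test. Noise is the only covariate. A risk factor that does not encode the instrument leaves the measurement part of the offset in place.

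**Formulas, linear model without a cohort term.**

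- False slope = δ·D·p(1−p) / v, with v = 1 + p(1−p)·D²
- SE = √[(s² + p(1−p)·δ²/v) / (N·v)]
- False-positive rate = 1 − Φ(1.96 − z) + Φ(−1.96 − z), with z = slope/SE

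**Worked case: δ = 0.5 mm, D = 0.25, s = 3 mm.** v = 1 + 0.247 × 0.0625 = 1.0154. Slope = 0.5 × 0.25 × 0.247/1.0154 = 0.0304 mm per SD of noise. SE = 0.0163. z = 1.87. Rate = 46.4%. With s = 4 mm, SE = 0.0217, z = 1.40 and the rate is 28.9%.

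| D | Offset (mm) | False slope (mm per SD) | Rate, s = 3 mm | Rate, s = 4 mm |
|---|---|---|---|---|
| 0.25 | 0 | 0 | 5% | 5% |
| 0.25 | 0.25 | 0.015 | 15.5% | 10.8% |
| 0.25 | 0.5 | 0.030 | 46.4% | 28.9% |
| 0.25 | 1 | 0.061 | 95.9% | 79.7% |
| 0.1 | 0.25 | 0.006 | 6.6% | 5.9% |
| 0.1 | 0.5 | 0.012 | 11.7% | 8.7% |
| 0.5 | 0.5 | 0.058 | 95.5% | 78.4% |

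With D = 0 the rate is 5% at any offset. Simulation at N = 33,723, s = 3 mm and D = 0.25 agrees: 15.0%, 46.3% and 96.4% for 0.25, 0.5 and 1 mm without a cohort term, and 4 to 6% with one.

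**AAA, by simulation.** The result depends on the assumed distribution. With normal diameters, 3% prevalence in the lower cohort, a 1 mm offset and D = 0.25, the false-positive rate is about 34 to 38% at s = 3 mm and about 20 to 24% at s = 4 mm. With a right-skewed distribution, 1 mm and D = 0.3, it is about 9%, against 79% for diameter in the same simulated data. AAA is less affected than diameter in each case.

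**Cost of a cohort term.** Without the term and with no offset, SE = s/√(N·v). With the term, SE = s/√N. The ratio √v is 1.001, 1.008, 1.030 and 1.117 for D = 0.1, 0.25, 0.5 and 1.

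**The case against.** The strongest reply is that this is a detail for the statistical analysis plan, which is not at hand. The Protocol names categories of confounder and not closed lists, its wider list is open-ended, and nothing forbids a cohort term. That would carry weight if the Protocol were silent on covariates. But it specifies confounders for these particular models, and both the named sets and the open list concern cardiovascular characteristics of the participant. Neither supplies a term for trial or instrument.

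A second reply is that pooling is inferred. That stands: the Protocol never says outright that the aortic models combine both trials, and a model restricted to one cohort would not have this problem. The single total, and the statement that traditional confounders were accounted for in all participants, point to both cohorts being used.

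A third is that the offset and the exposure difference are both undocumented. That also stands. Different regions need not have different mean noise, and the table shows sensitivity to chosen inputs, not an observed bias.

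Finally, a cohort term gives up the between-region contrast in noise, including any true effect expressed through it. That is a real trade-off, and it is the reason to report diameter both ways.

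A reader might infer more than this. The imaging argument does not reach PAD or ABI, which share one Doppler method, or CAC, for which CT is described only in DANCAVAS. Nor does it reach the primary Cox analysis, which uses register outcomes and names inclusion date. A reader might also take the approval reference numbers to show that the cohorts were examined years apart. The Protocol gives no inclusion dates, so that is not relied on.

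**Conclusion.** The point holds as a gap in the specification of the noise models for aortic diameter and, to a lesser degree, AAA. The text names no cohort term, and imaging method follows cohort exactly on the screening described. If both cohorts are modelled together, any offset in measured diameter combined with any cohort difference in mean noise biases the noise slope, and the named risk factors cannot remove a measurement offset.

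The size is unknown. Over assumed offsets of 0 to 1 mm and exposure differences of 0 to 0.5 SD, the false-positive rate for diameter runs from 5% to 100%, and the documents cannot place the study within that range. The false slopes are small in millimetres. They matter because the standard error is only about 0.016 to 0.022 mm per SD of noise.

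It would go too far to say that a bias has been shown, or that the primary analysis is affected: the documents report neither of the two differences it needs. This is a worthwhile, cheap correction to supporting analyses, held with medium confidence.

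**What to change.** Add a trial-cohort term (VIVA v DANCAVAS) to the noise models for aortic diameter and AAA. Alternatively, fit them within each cohort and combine the two slopes. Report the diameter result with and without the term, so that the contribution of the between-cohort contrast is visible.

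The cost is one model term from data already held. The between-region exposure contrast is given up, and the standard error rises by about 0.1% to 3% for cohort exposure differences of 0.1 to 0.5 SD, and by about 12% at 1 SD.

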This study will provide more detailed data as we can model pollution levels hourly compared to the MESA Air's two-week periods. Furthermore, we will incorporate work addresses where previous studies are limited to home addresses only. The MESA Air study is the most comprehensive to date but limited as they divide the contributions into PM_{2.5} and NO_x only. Previous studies have provided air pollution data as an accumulated amount where we have the possibility to show if the air pollution is of local origin (e.g., traffic, wood stoves), national origin (e.g., power plants, industries, agriculture), or international origin (e.g., other countries, shipping). We can show which component contributes most and where the pollutant(s) comes from.

The American Journal of Hypertension released a call for clinical trials on the correlation between air pollution and CVD in 2018 (35), and a joint opinion was released in April 2021 by the World Heart Federation, American College of Cardiology, American Heart Association, and the European Society of Cardiology due to the increasing concern about air pollution in the development of cardiovascular disease (36). They state that *50% of the 6,7 million deaths that can be attributed to air pollution are due to CVD* (36), which is concerning due to the fact that the disease burden of air pollution seems to be “larger and higher-ranking” than some of the presently recognized CVD risk factors (37).

We published a method article in 2020 (38) accounting for the aims of our study and the release of the concerning joint opinion in Circulation has reinforced the importance of this study. Hence, this project will contribute with unique and precise data to show if a correlation between air pollution and CVD burden truly exists.

Another aspect of environmental risk factors is environmental noise. The first article about this subject was published in 1985, nevertheless, it is only in recent years we are seeing both growing quality and quantity of articles in esteemed

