journals about environmental noise. These articles unanimously report an increased risk of hypertension, coronary heart disease, stroke, heart failure and atrial fibrillation with even slightly increased levels of environmental noise (specifically road traffic noise and aircraft noise). One of these studies (39) was a cross-sectional study of residents in London who lived close to Heathrow Airport. The study found an increased relative risk for admission due to coronary heart disease and CVD. Another study relating to another cardiovascular complication, hypertension, found that long-term residential exposure to noise was associated with increased incidence of (self-reported) hypertension (40).

HYPOTHESIS

The purpose of this study is to determine the impact of individually accumulated exposure to air and noise pollution, as well as exposure fluctuations (peaks), on the incidence and prevalence of CVD. Noise pollution can be a significant confounder for the relation investigated and we will therefore include accumulated data for noise over time together with air pollution data.

The ICD or SKS disease classification code system will be used to identify clinical events for patients from the two trials (described below). CVD mortality and total mortality as well as clinical events from myocardial infarctions, percutaneous coronary interventions, coronary artery bypass grafts, heart failure, apoplexies, and bypass will be examined. The analysis will be stratified by socioeconomic status to determine if there is a social inequality in the air and noise pollution impact.

We will examine the individual air pollution exposure as well as noise exposure to understand each pollutants' contribution to the accumulated risk and demonstrate the impact of air and noise pollution on CVD morbidity and mortality. We hypothesize that:

1. the amount of accumulated air as well as noise pollution is a highly independent significant risk factor for clinical CVD, when accounting for all traditional cardiovascular risk factors.
2. certain subdivisions of the air pollution exposure carry the highest contribution for development of clinical CVD. This will provide novel and valuable information as this has never been investigated with the precision we can deliver.
3. accumulated air and noise pollution from both individual home addresses and work addresses together better predicts clinical CVD than models based solely on home addresses. No study has evaluated this before.

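### Hypothesis 3 (home plus work versus home-only exposure) rests on a ROC comparison alone; add a nested likelihood-ratio test beside it

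*Protocol*

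**What the plan says.** Hypothesis 3 (Protocol, HYPOTHESIS, item 3) states that "accumulated air and noise pollution from both individual home addresses and work addresses together better predicts clinical CVD" than models using home addresses only, and adds that no study has evaluated this. BACKGROUND presents work addresses as an advance: "we will incorporate work addresses where previous studies are limited to home addresses only".

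The analysis is in METHOD, Statistics: "we will compare regression models with accumulated air pollution from both work and home addresses with models with air pollution only from home addresses". The next sentence gives the criterion: "ROC curves from both models will be compared to evaluate the hypothesis". For this hypothesis the section names no test of the work coefficient, no likelihood-ratio test and no test for the ROC difference. It does not say whether work exposure is a separate term or is added to home exposure to form one total.

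For the clinical outcomes the same section says "Primarily a multivariate Cox proportional hazards regression model will be used", "when adjusting for inclusion date, sex, and other potential confounding factors at baseline".

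**The concern.** A ROC comparison asks whether discrimination improves. That fits a hypothesis about prediction, but it is an insensitive way to find out whether a new variable carries any information. When the added term has no effect, the two fitted linear predictors are nearly identical. The AUC difference and its variance then both shrink towards zero, and the usual normal reference for a paired AUC test no longer fits. The test rejects far below its nominal level, and the loss carries over into power for small effects.

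With the ROC comparison as the only criterion, a small but real contribution of work-address exposure could be reported as absent, although the planned Cox model on the same data might show it clearly. Only hypothesis 3 is exposed to this.

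**Working it through.** The protocol gives no power, event count or effect size for hypothesis 3, so there is no stated figure to reproduce. The check compares the two tests on simulated cohorts.

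**From the protocol.** n = 33,723 (METHOD, Study population: "A total of 33,723 participants in the age of 60-74 are included from the two cohorts") and Cox regression as the main model.

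**Assumed.** Two-sided 5% level; 15% events (5% to 20% as a range); equal follow-up for all; a risk score giving a baseline AUC of about 0.70; home-work correlation 0.3 to 0.7; work hazard ratio (HR) 1.00 to 1.10 per SD given home; a DeLong test for the AUC difference.

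**Analytic check of the Cox test.** Power = Φ(√(D(1 − ρ²)) × ln HR − 1.96), where D is the number of events.

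- 15% events: D = 0.15 × 33,723 = 5,058. With ρ = 0.5, √(5,058 × 0.75) = 61.6. At HR 1.05, 61.6 × 0.0488 = 3.00, and Φ(3.00 − 1.96) is about 85%.
- 5% events: D = 1,686. √(1,686 × 0.75) = 35.6, 35.6 × 0.0488 = 1.74, and Φ(1.74 − 1.96) is about 41%.

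**Simulation A: work as its own term, 15% events** (800 cohorts per scenario; Monte Carlo standard error at most 2.0 points, including the sensitivity runs). Each cell gives the rejection rate of DeLong versus the Cox likelihood-ratio test (LRT).

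| Work HR per SD | ρ = 0.3 | ρ = 0.5 | ρ = 0.7 | AUC gain (ρ = 0.3 / 0.5 / 0.7) |
|---|---|---|---|---|
| 1.00 | 0.5% vs 5.8% | 0.4% vs 5.0% | 0.3% vs 4.1% | – |
| 1.05 | 24% vs 88% | 15% vs 84% | 9% vs 69% | 0.0005 / 0.0004 / 0.0003 |
| 1.10 | 92% vs 100% | 86% vs 100% | 63% vs 99.9% | 0.0016 / 0.0013 / 0.0009 |

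Sensitivity at HR 1.05 and ρ = 0.5 (650 cohorts each): moving events from 10% to 20% gives 8% to 27% for DeLong versus 71% to 93% for the LRT. Moving the risk-score HR from 1.5 to 3 gives 18% to 13% versus 84% to 86%.

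**Simulation B: same question, separately programmed** (700 cohorts per setting, ρ = 0.5, home HR 1.10).

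| Work HR per SD | 15% events, DeLong vs LRT | 5% events, DeLong vs LRT |
|---|---|---|
| 1.00 | 0.3% vs 4.4% | 0.6% vs 5.7% |
| 1.03 | 3% vs 43% | 1% vs 17% |
| 1.05 | 15% vs 86% | 3% vs 38% |
| 1.08 | 58% vs 99.9% | 12% vs 77% |
| 1.10 | 86% vs 100% | 24% vs 91% |

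The simulated LRT power agrees with the formula to within about 3 points. A one-sided DeLong test at 5% does not repair the conservatism: it rejects in about 1% when work has no effect.

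**Simulation C: logistic models** (about 14% events, ρ = 0.5). With no work effect, DeLong rejects in 1% and the LRT in 5%. At an effect of 1.05 per SD, power is 15% versus 81%.

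**If the true exposure is a weighted sum of home and work.** The summed model and the home-only model are not nested, so the LRT compares home plus a separate work term with home alone. ROC results count only when they favour the sum; ρ = 0.5.

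| Setting | ROC favours sum | LRT rejects |
|---|---|---|
| A, 75/25 weights, HR 1.05 per SD of the sum | 3% | 14% |
| A, 75/25, HR 1.10 | 10% | 38% |
| A, 75/25, HR 1.15 | 19% | 69% |
| A, 60/40, HR 1.10 | 22% | 80% |
| C, 60/40, effect 1.10 | 17% | 72% |
| C, 50/50, effect 1.10 | 32% | 92% |
| B, equal sum, HR 1.05 each for home and work, 15% events | 19% | 80% |

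AUC gains in the 75/25 runs are 0.00003, 0.0001 and 0.0002. When home exposure alone is the truth, the LRT rejects in 4% to 7%. A rule preferring the sum when its AIC is lower by more than 2 picks it wrongly in 3% to 9%, so that rule is not a 5% test.

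**The case against.** The strongest reply is that the LRT answers a neighbouring question. Hypothesis 3 is about better prediction, ROC curves measure exactly that, and a significant LRT with an AUC gain of 0.0004 does not show better prediction in any useful sense. This stands: the LRT should not replace the ROC comparison, and by itself it supports only a statement about added information.

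Second, the largest figures depend on a separate work term and a DeLong-type test, and the protocol states neither. An accumulated exposure from both addresses can just as well be one total. This also stands as a condition. On the summed reading with a 75/25 split and a small effect, both methods are weak (3% versus 14%). The direction does not change, however, and with a heavier work share the gap is again large (22% versus 80% at 60/40).

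Third, a statistical analysis plan that is not at hand may add a test, and nothing in the protocol forbids reporting the work coefficient. True, but the protocol does fix a criterion for this hypothesis, and the comment concerns that choice rather than a missing detail.

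Fourth, the error is in the cautious direction: too few positive claims, with no effect on the primary analysis. That limits the weight of the point but does not remove it.

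**Conclusion.** The concern holds. As written, hypothesis 3 is decided by a comparison of ROC curves and nothing else. With a separate work term and a DeLong-type test, that comparison rejects in about 1% or less under no effect. At HR 1.05 per SD with 15% events it has 9% to 24% power, against 69% to 88% for the likelihood-ratio test, depending on the home-work correlation. At HR 1.10 with 15% events and ρ = 0.5 the gap narrows to 86% versus 100%.

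Only n comes from the protocol. Event rate, correlation, effect size, exposure form, ROC test, equal follow-up and usable work exposure for everyone are assumptions, so the direction is firm and the size is not. The AUC gain stays below 0.002 throughout, so a conclusion of no material gain in prediction may well be right. What the present plan could miss is that work exposure carries information beyond home exposure. This is a worthwhile, inexpensive improvement to a stated hypothesis; the primary Cox analysis is not affected.

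**What to change.** - In the planned Cox model, keep home exposure, add work exposure as a separate term, and name the 1-df likelihood-ratio test as the test of added information. Report the work hazard ratio with its confidence interval. This can be done even if a summed exposure is also reported.
- Keep discrimination as the measure of prediction: the difference in C-index, or in time-dependent AUC at a fixed horizon, with a confidence interval. Use a censoring-aware form, because follow-up ends on one date ("The entire study population is monitored until December 31. 2022, in the Danish national registers") while inclusion dates vary and are adjusted for.
- State the reading rule in advance. Better prediction is claimed only if the discrimination difference supports it; if only the likelihood-ratio test is significant, the report says that work exposure adds information.
- Treat any AIC comparison of summed and home-only models as descriptive.

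The cost is two or three sentences and one extra Cox model on data already planned. The downside is two results that may point in different directions, which the reading rule is there to handle.
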